### **7.2.3.3 Protocol-Specific Exceptions to Serious Adverse Event Reporting**

Efficacy endpoints as outlined in this section will not be reported to the Sponsor as described in Section 7.2.3 - Immediate Reporting of Adverse Events to the Sponsor.

Specifically, the suspected/actual events covered in this exception include any event that is disease progression of the cancer under study.

The Sponsor will monitor unblinded aggregated efficacy endpoint events and safety data to ensure the safety of the subjects in the trial. Any suspected endpoint which upon review is not progression of the cancer under study will be forwarded to global safety as a SAE within 24 hours of determination that the event is not progression of the cancer under study.

### **7.2.4 Evaluating Adverse Events**

An investigator who is a qualified physician will evaluate all adverse events according to the NCI Common Terminology for Adverse Events (CTCAE), version 4.0. Any adverse event which changes CTCAE grade over the course of a given episode will have each change of grade recorded on the adverse event case report forms/worksheets.

All adverse events regardless of CTCAE grade must also be evaluated for seriousness.

Table 12: Evaluating Adverse Events

An investigator who is a qualified physician, will evaluate all adverse events as to:

V4.0 CTCAE Grading	Grade 1	Mild; asymptomatic or mild symptoms; clinical or diagnostic observations only; intervention not indicated.
	Grade 2	Moderate; minimal, local or noninvasive intervention indicated; limiting age-appropriate instrumental ADL.
	Grade 3	Severe or medically significant but not immediately life-threatening; hospitalization or prolongation of hospitalization indicated; disabling; limiting self-care ADL.
	Grade 4	Life threatening consequences; urgent intervention indicated.
	Grade 5	Death related to AE
Seriousness	A serious adverse event is any adverse event occurring at any dose or during any use of Sponsor's product that:	
	† Results in death ; or	
	† Is life threatening ; or places the subject, in the view of the investigator, at immediate risk of death from the event as it occurred (Note: This does not include an adverse event that, had it occurred in a more severe form, might have caused death.); or	
	† Results in a persistent or significant disability/incapacity (substantial disruption of one's ability to conduct normal life functions); or	
	† Results in or prolongs an existing inpatient hospitalization (hospitalization is defined as an inpatient admission, regardless of length of stay, even if the hospitalization is a precautionary measure for continued observation. (Note: Hospitalization for an elective procedure to treat a pre-existing condition that has not worsened is not a serious adverse event. A pre-existing condition is a clinical condition that is diagnosed prior to the use of a Merck product and is documented in the patient's medical history.); or	
	† Is a congenital anomaly/birth defect (in offspring of subject taking the product regardless of time to diagnosis); or	
	Is a new cancer (that is not a condition of the study) (although not serious per ICH definition, is reportable to the Sponsor within 24 hours to meet certain local requirements); or	
	Is an overdose (whether accidental or intentional). Any adverse event associated with an overdose is considered a serious adverse event for collection purposes. An overdose that is not associated with an adverse event is considered a non-serious event of clinical interest and must be reported within 24 hours.	
	Other important medical events that may not result in death, not be life threatening, or not require hospitalization may be considered a serious adverse event when, based upon appropriate medical judgment, the event may jeopardize the subject and may require medical or surgical intervention to prevent one of the outcomes listed previously (designated above by a †).	
Duration	Record the start and stop dates of the adverse event. If less than 1 day, indicate the appropriate length of time and units	
Action taken	Did the adverse event cause the Sponsor's product to be discontinued?	
Relationship to Sponsor's Product	Did the Sponsor's product cause the adverse event? The determination of the likelihood that the Sponsor's product caused the adverse event will be provided by an investigator who is a qualified physician. The investigator's signed/dated initials on the source document or worksheet that supports the causality noted on the AE form, ensures that a medically qualified assessment of causality was done. This initialed document must be retained for the required regulatory time frame. The criteria below are intended as reference guidelines to assist the investigator in assessing the likelihood of a relationship between the test drug and the adverse event based upon the available information. The following components are to be used to assess the relationship between the Sponsor's product and the AE; the greater the correlation with the components and their respective elements (in number and/or intensity), the more likely the Sponsor's product caused the adverse event (AE):	
	Exposure	Is there evidence that the subject was actually exposed to the Sponsor's product such as: reliable history, acceptable compliance assessment (pill count, diary, etc.), expected pharmacologic effect, or measurement of drug/metabolite in bodily specimen?
	Time Course	Did the AE follow in a reasonable temporal sequence from administration of the Sponsor's product? Is the time of onset of the AE compatible with a drug-induced effect (applies to trials with investigational medicinal product)?
	Likely Cause	Is the AE not reasonably explained by another etiology such as underlying disease, other drug(s)/vaccine(s), or other host or environmental factors

Relationship to Sponsor's Product (continued)	The following components are to be used to assess the relationship between the test drug and the AE: (continued)	
	Dechallenge	Was the Sponsor's product discontinued or dose/exposure/frequency reduced? If yes, did the AE resolve or improve? If yes, this is a positive dechallenge. If no, this is a negative dechallenge. (Note: This criterion is not applicable if: (1) the AE resulted in death or permanent disability; (2) the AE resolved/improved despite continuation of the Sponsor's product; or (3) the trial is a single-dose drug trial; or (4) Sponsor's product(s) is/are only used one time.)
	Rechallenge	Was the subject re-exposed to the Sponsor's product in this study? If yes, did the AE recur or worsen? If yes, this is a positive rechallenge. If no, this is a negative rechallenge. (Note: This criterion is not applicable if: (1) the initial AE resulted in death or permanent disability, or (2) the trial is a single-dose drug trial); or (3) Sponsor's product(s) is/are used only one time). NOTE: IF A RECHALLENGE IS PLANNED FOR AN ADVERSE EVENT WHICH WAS SERIOUS AND WHICH MAY HAVE BEEN CAUSED BY THE SPONSOR'S PRODUCT, OR IF REEXPOSURE TO THE SPONSOR'S PRODUCT POSES ADDITIONAL POTENTIAL SIGNIFICANT RISK TO THE SUBJECT, THEN THE RECHALLENGE MUST BE APPROVED IN ADVANCE BY THE SPONSOR CLINICAL DIRECTOR AS PER DOSE MODIFICATION GUIDELINES IN THE PROTOCOL.
	Consistency with Trial Treatment Profile	Is the clinical/pathological presentation of the AE consistent with previous knowledge regarding the Sponsor's product or drug class pharmacology or toxicology?
The assessment of relationship will be reported on the case report forms /worksheets by an investigator who is a qualified physician according to his/her best clinical judgment, including consideration of the above elements.		
Record one of the following	Use the following scale of criteria as guidance (not all criteria must be present to be indicative of a Sponsor's product relationship).	
Yes, there is a reasonable possibility of Sponsor's product relationship.	There is evidence of exposure to the Sponsor's product. The temporal sequence of the AE onset relative to the administration of the Sponsor's product is reasonable. The AE is more likely explained by the Sponsor's product than by another cause.	
No, there is not a reasonable possibility of Sponsor's product relationship	Subject did not receive the Sponsor's product OR temporal sequence of the AE onset relative to administration of the Sponsor's product is not reasonable OR the AE is more likely explained by another cause than the Sponsor's product. (Also entered for a subject with overdose without an associated AE.)	

### 7.2.5 Sponsor Responsibility for Reporting Adverse Events

All Adverse Events will be reported to regulatory authorities, IRB/IECs and investigators in accordance with all applicable global laws and regulations, i.e., per ICH Topic E6 (R1) Guidelines for Good Clinical Practice.

## 8.0 STATISTICAL ANALYSIS PLAN

This section outlines the statistical analysis strategy and procedures for the study. If, after the study has begun, but prior to final database lock, changes made to primary and/or key secondary hypotheses, or the statistical methods related to those hypotheses, then the protocol will be amended (consistent with ICH Guideline E-9). Changes to exploratory or other non-confirmatory analyses made after the protocol has been finalized, but prior to final database lock, will be documented in a supplemental statistical analysis plan (sSAP) and referenced in the Clinical Study Report (CSR) for the study. Post hoc exploratory analyses will be clearly identified in the CSR. Separate analysis plans (i.e., separate documents from the sSAP) will be developed to detail other planned analyses (i.e., those specific to the analysis of PK data, and future biomedical research).

### 8.1 Statistical Analysis Plan Summary

Key elements of the statistical analysis plan are summarized below; the comprehensive plan is provided in subsequent sections.

Study Design Overview	A Phase IB Dose Exploration Trial with MK-8628, a Small Molecule Inhibitor of the Bromodomain and Extra-Terminal (BET) Proteins, in Subjects with Selected Advanced Solid Tumors
Treatment Assignment	This is an open label study with dose level specific cohorts.
Analysis Populations	Efficacy: Treatment Full Analysis Set (FAS), which is the same as ASaT Safety: DLT evaluable, and All Subjects as Treated (ASaT)
Primary Endpoint(s)	Proportion of subjects experiencing at least one DLT in cycle 1 (day 1 to 21)
Secondary Endpoints	ORR, DOR and DCR based on the best overall response from tumor evaluations performed every 2 cycles, according to RECIST v1.1 or PCWG2 as assessed by investigator radiologic review.
Statistical Methods for Key Efficacy/Immunogenicity/ Pharmacokinetic Analyses	ORR and DCR will be estimated using an exact method based on the binomial distribution (Clopper-Pearson interval).
Statistical Methods for Key Safety Analyses	Counts and percentage of DLT will be provided. 80% Bayesian credible interval for DLT rate will be estimated based on a prior distribution of Beta(1,1).
Interim Analyses	During the dose escalation phase, regular assessment of data from the most recent cohort of subjects evaluable for DLT will be performed.
Multiplicity	This is an estimation study and no multiplicity adjustment will be implemented
Sample Size and Power	The study is designed to assess the safety of MK-8628 in subjects with advanced or metastatic solid tumors. The small numbers per cohort are not intended for statistical hypotheses.  Up to 72 evaluable subjects (up to 6-14 per three dose levels in the dose escalation part [Part A] and up to 30 in the NMC cohort [Part B]) will be included. The final sample size will depend on the number of subjects experiencing DLTs at each DL, and may be increased if the RP2D is not reached and additional DLs are required.

## **8.2 Responsibility for Analyses/In-House Blinding**

The statistical analysis of the data obtained from this study will be the responsibility of the Clinical Biostatistics department of the SPONSOR.

This trial is being conducted as an open-label study with dose level-specific cohorts.

## **8.3 Hypotheses/Estimation**

Objectives of the study are stated in Section 3.0.

There are no statistical hypotheses for this study.

## **8.4 Analysis Endpoints**

### **8.4.1 Safety Endpoints**

The primary safety objective of this trial is to estimate Proportion of subjects experiencing at least one DLT in cycle 1 (day 1 to 21) for each of the dose level-specific cohorts.

Other safety endpoints include Incidence, severity and relationship of AEs, laboratory abnormalities, SAEs, discontinuations due to AEs, dose adaptations due to AEs.

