#### **5.2.1.2 Dose Escalation (Part A)**

A twice daily (BID) dose escalation will be performed using a 6+8 two-stage design with continuous DLT rate monitoring via a modified toxicity probability index (mTPI) (Ji design), targeting a maximum 25% DLT rate [1].

Starting from 20 mg BID, up to three planned dose levels may be evaluated: 20 mg BID, 30 mg BID 40 mg BID (all continuous daily). See [Table 4](#) and [Table 5](#) for the dose escalation scheme.

Table 4: Dose Escalation Scheme

Dose Level (DL)	MK-8628 (mg/dose)	Outcome (#DLT/#Subjects)* / Actions to be taken
	BID Regimen (continuous)	
DL 1	20	At each DL: - Escalate/de-escalate per DLT rate observed using mTPI Table ( Table 5 )
DL 2	30	
DL 3	40	

\* Evaluated during the first 21 days of treatment

Table 5: Modified Toxicity Probability Interval (mTPI) Design

Number of toxicities	Number of subjects treated at current dose								
	6	7	8	9	10	11	12	13	14
0	E	E	E	E	E	E	E	E	E
1	S	E	E	E	E	E	E	E	E
2	S	S	S	S	S	S	S	S	E
3	D	S	S	S	S	S	S	S	S
4	DU	DU	DU	D	S	S	S	S	S
5	DU	DU	DU	DU	DU	D	S	S	S
6	DU	DU	DU	DU	DU	DU	DU	DU	D
7		DU	DU	DU	DU	DU	DU	DU	DU
8			DU	DU	DU	DU	DU	DU	DU
9				DU	DU	DU	DU	DU	DU
10					DU	DU	DU	DU	DU
11						DU	DU	DU	DU
12							DU	DU	DU
13								DU	DU
14									DU

E = Escalate to the next higher dose  
S = Stay at the current dose  
D = De-escalate to the next lower dose  
DU = The current dose is unacceptably toxic  
Target toxicity rate = 25%

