### 5.2.1.4 Dose Limiting Toxicity

For the dose escalation part of this study (Part A), a DLT is defined as any of the following toxicities occurring during the first cycle of treatment (21 days) for each dose level. See Section 5.9 for rules on replacement of subjects in the DLT period.

The occurrence of any of the following toxicities during Cycle 1, **if assessed by the investigator to be possibly, probably or definitely related to MK-8628**, will be considered a DLT:

Hematologic toxicity

- Grade 4 hematologic toxicity lasting  $\geq 7$  days, except thrombocytopenia
  - Grade 4 thrombocytopenia of any duration
  - Grade 3 thrombocytopenia is a DLT if associated with bleeding
- Febrile neutropenia Grade 3 or Grade 4

Non-hematologic toxicity

- Grade 4 non-hematologic toxicity (not laboratory)
- Grade 3 non-hematologic toxicity (not laboratory) lasting  $> 3$  days despite optimal supportive care. Grade 3 nausea, vomiting or diarrhea will be considered a DLT if lasting more than 3 days despite optimal supportive care.
- Any Grade 3 or 4 non-hematologic laboratory abnormality, if:
  - medical intervention is required, or
  - the abnormality leads to hospitalization, or
  - the abnormality persists for  $> 1$  week
- Any of the following liver test abnormalities are observed (see also Section 12.7):
  - ALT or AST  $> 8X$  ULN
  - ALT or AST  $> 5X$  ULN for more than 2 weeks
  - ALT or AST  $> 3X$  ULN **AND** (total bilirubin  $> 2X$  ULN **OR** INR  $> 1.5$ )
  - ALT or AST  $> 3X$  ULN with the appearance of fatigue, nausea, vomiting, right upper quadrant pain or tenderness, fever, rash and/or eosinophilia ( $> 5\%$ ), unless the investigator assesses the rash or fatigue to be related to MK-8628 and not related to liver impairment, with Sponsor's agreement

Other

- Any drug-related AE which caused the subject to discontinue treatment during Cycle 1
- Any study drug-related toxicity resulting in a subject missing  $\geq 20\%$  of planned doses during Cycle 1.
- Any treatment-related toxicity which causes a greater than 2 week delay in initiation of Cycle 2.
- Grade 5 toxicity

DLTs must be reported within 24 hours to the Sponsor as Events of Clinical Interest (see Section 7.2.3.2). If the event also meets the criteria for seriousness, follow the reporting guidelines for Serious Adverse Events (SAEs) outlined in Section 7.2.3.1.

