### **5.2.2 Timing of Dose Administration**

MK-8628 is to be administered orally with water in a fasted state, and as part of a BID regimen (twice daily, approximately 12±2 hours apart). The definition of a fasted state is that subjects should not have food for 1 hour before or 3 hours after study drug administration.

Dosing not performed at the same time (±2h) as on other days will be skipped. Subjects are to be instructed that if they vomit or skip their dose in that time frame, it is not to be replaced.

Capsules must not be opened or chewed.

A treatment cycle is 21 days (3 weeks). The subsequent cycle will begin on day 22 or after recovery from any AEs to baseline or Grade < 2 associated with the previous cycle.

Subjects should receive study treatment within 3 days following registration.

Details of the exact dose and time of administration will be documented in a validated subject diary and reported in the electronic case report form (eCRF).

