Adverse Events Monitoring		X	X	X	X	X	X	X	X	X	X	X g	X g
Laboratory Procedures/Assessments													
Complete Blood Count (CBC) h	X l	X l	X	X	X	X	X	X h	X h,j	X h,j		X	
Serum Chemistry h	X l	X l		X		X		X h	X h,j	X h,j		X	
PT (INR), aPTT and Factor VII	X	X l		X		X							
Urinalysis	X												
Urine Pregnancy Test – if applicable k	X												
Tumor markers l	X l	X l						X				X l	X l
PK Blood (Plasma) Sampling		X m		X n		X n							
PD Blood Sampling		X o		X o									
Blood for Genetic Analysis p		X											

- a. In subjects who discontinue study therapy without documented disease progression, every effort should be made to continue monitoring their disease status by radiologic imaginge,f \* every 6 weeks  $\pm$  3 days until (1) the start of new anti-cancer treatment, (2) documented disease progression, (3) death, or (4) the end of the study, whichever occurs first. \*Note: This includes bone scans for CRPC subjects every 12 weeks  $\pm$  3 days. If subjects have stable disease, partial response, or complete response, they should continue on this assessment schedule. The timing for these assessments should continue the same imaging schedule from the treatment phase; Imaging, and if applicable, bone scans, should occur at any time where there is clinical suspicion of progression;
- b. For study subjects who are legal minors, the parent or legal guardian must also sign the consent/assent form;
- c. MK-8628 is to be administered orally with water in a fasted state, and as part of a BID regimen (twice daily, approximately 12 $\pm$ 2 hours apart). Dosing not performed at the same time ( $\pm$ 2h) as on other days will be skipped. Subjects are to be instructed that if they vomit or skip their dose in that time frame, it is not to be replaced;
- d. On Cycle 1 Day 1, conduct 12-lead ECG immediately before intake of the morning study dose, then again 1 and 2 hours after the intake of the morning study dose. Conduct additional 12-lead ECGs immediately before the morning intake on Day 1 of odd subsequent cycles (e.g. Cycle 3, 5, 7 etc.);

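### The DLT window closes on Day 21, but chemistry/INR are last scheduled at the Day 15 visit and CBC at the Day 18 visit, and the plan does not assign the Cycle 2 Day 1 laboratory findings to Cycle 1, so the DLT rate can be biased down.

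*Combined protocol and SAP*

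**What the plan says.** The 21-day limit appears in several places. Section 8.4.1 (and the summary in 8.1) gives the primary endpoint as "Proportion of subjects experiencing at least one DLT in cycle 1 (day 1 to 21". The footnote to Table 4 in 5.2.1.2, which governs escalation, says "Evaluated during the first 21 days of treatment". Section 5.2.1.4 defines a DLT as "any of the following toxicities occurring during the first cycle of treatment (21 days) for each dose level".

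The flow chart in 6.0 sets the Cycle 1 laboratory days:

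- "Complete Blood Count (CBC"): Days 1, 4, 8, 11, 15 and 18.
- "Serum Chemistry": Days 1, 8 and 15.
- "PT (INR), aPTT and Factor VII": Days 1, 8 and 15.

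The Day 15 and Day 18 visits each carry a ±3-day window. The next scheduled set is Cycle 2 Day 1. Section 5.2.2 states "The subsequent cycle will begin on day 22", or later if adverse events have not recovered.

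Section 5.2.1.4 lists laboratory criteria with no duration: Grade 4 thrombocytopenia, ALT or AST above 8 times ULN, and ALT or AST above 3 times ULN together with raised bilirubin or INR. It also counts a treatment-related delay of Cycle 2 by more than 2 weeks. Section 8.5.2 makes a subject DLT-evaluable after 85% of planned dosing (18 days) or a DLT. It requires no end-of-cycle laboratory sample.

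**The concern.** The endpoint window and the sampling schedule do not end together. A Grade 4 platelet count drawn on Day 20 is a DLT at once. The same count first drawn on Day 22, before the Cycle 2 dose, follows only Cycle 1 dosing, yet it has no stated place in an endpoint limited to Days 1 to 21. The one criterion that expressly refers to the start of Cycle 2 needs a delay of more than 2 weeks, so a shorter event does not meet it.

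The DLT rate drives each Table 5 decision and carries most weight in selecting the RP2D (5.2.1.5). Laboratory toxicity is also the main type seen so far. Section 4.1.3 describes six DLTs in the earlier solid-tumor study: four were thrombocytopenia and one was hyperbilirubinemia/transaminitis. If findings of this kind at the end of Cycle 1 are left out, the counted rate falls below the true Cycle 1 rate. If investigators date them differently, identical results are classified differently in the primary endpoint.

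**Working it through.** **The plan's own figures.** An mTPI rule with a Beta(1,1) prior, target 0.25, interval half-widths of 0.05 and an unacceptable-toxicity cut-off of 0.95 reproduces every Table 5 cell for 0 to 6 toxicities and n = 6 to 14. The half-widths and cut-off are assumptions, since the plan does not give them. No stated figure is in dispute.

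**Uncovered days at the end of the window (6.0).**

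- Chemistry/INR, nominal: Days 16–21, 6/21 = 0.286. The Day 15 visit may fall on Day 12 to 18, so the tail is 21 − 18 = 3 to 21 − 12 = 9 days. It is never zero.
- CBC, nominal: Days 19–21, 3/21 = 0.143. The Day 18 visit may fall on Day 15 to 21, so the tail is 0 to 6 days.

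**Effect on the counted rate.** Let f be the share of DLTs first detectable after the last in-window sample and not counted. The counted rate is q = p(1 − f). On nominal days with uniform onset, f = 1/7 if all DLTs are CBC-based and f = 2/7 if all are chemistry-based. For p = 0.25, P(0/6) = (1 − q)^6 and P(≥3/6) is the binomial tail:

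| f | q | P(0/6), escalate | P(≥3/6), de-escalate or unacceptable |
|---|---|---|---|
| 0 | 0.250 | 0.178 | 0.169 |
| 1/7 | 0.214 | 0.235 | 0.117 |
| 2/7 | 0.179 | 0.307 | 0.074 |

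**A mix taken from the documents.** Use the six DLTs in 4.1.3: 4/6 CBC-based, 1/6 chemistry-based, 1/6 clinical.

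- Nominal visits: f = (4/6)(3/21) + (1/6)(6/21) = 18/126 = 1/7, the middle row.
- Latest permitted visits: f = (4/6)(0) + (1/6)(3/21) = 0.024, so q = 0.244 and P(0/6) = 0.756^6 = 0.187.
- Earliest permitted visits for every subject: f = (4/6)(6/21) + (1/6)(9/21) = 33/126 = 0.262, so q = 0.185 and P(0/6) = 0.8155^6 = 0.294.

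These all lie within 0 to 2/7. The mix is only an illustration. That study dosed once daily, and two of its four thrombocytopenia DLTs were prolonged Grade 3, which 5.2.1.4 here lists only when there is bleeding.

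**Effect on a Table 5 decision.** At n = 6, one uncounted event turns 3/6 (D) into 2/6 (S) and 1/6 (S) into 0/6 (E). At the starting dose level, D stops the trial. Going from 2/6 to 1/6 changes nothing (both S). At larger n an uncounted event often changes nothing: 3/7 and 2/7 are both S, as are 3/8 and 2/8, and 4/10, 3/10 and 2/10.

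**The case against.** The strongest reply is that 5.2.1.4 speaks of toxicity occurring in Cycle 1, not of its detection. An investigator could date a Day 22 finding back to Cycle 1, and nothing forbids it. Several criteria (at least 7 days, more than 1 week, more than 2 weeks) already require follow-up that can run past Day 21. This stands as far as it goes: a reader might infer that the plan expressly excludes Day 22 findings, and it does not. But no rule includes them either, and the literal Day 1 to 21 wording favors leaving them out.

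Second, other checks exist. Section 7.1 allows unscheduled tests, and adverse events are reviewed at the Day 18 visit. Section 5.6.1.2 requires weekly monitoring of abnormal liver tests, and 12.7.3 requires two or three tests weekly once the potential-DILI criteria are met. These catch some events, so a reader who infers that late laboratory toxicity is systematically missed goes too far. The checks are incomplete, though. They depend on judgment or on an abnormality already seen, and weekly retesting from Day 15 falls on 15 + 7 = Day 22.

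Third, a reader might infer that a true 35% rate would be seen as 25%, since 0.35 × 15/21 = 0.25. That requires every DLT to be chemistry-based, uniform onset and no unscheduled test. The mix in 4.1.3 contradicts the first condition; on that mix and nominal visits the figure is 0.35 × 6/7 = 0.30, still assuming every late event is dropped.

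Fourth, pre-dose collection of safety laboratories is written for Cycle 1 Day 1 only (flow chart footnote). For Day 22, 7.1.3.2.1 requires the morning dose to be withheld for the PK sample, and 7.1.2.2 puts the physical exam before dosing. Pre-dose safety sampling is therefore likely in practice but not stated.

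Finally, a 21-day window matching the cycle is a legitimate choice. The point is only that its last days are not fully sampled and the next sample is unassigned.

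**Conclusion.** The point holds as a mismatch between the endpoint window and the laboratory schedule that can bias the DLT rate downward. It does not show a bias of known size. The chemistry/INR gap of 3 to 9 days exists under any permitted visit timing; the CBC gap of 0 to 6 days can vanish.

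If between none and 2/7 of DLTs go uncounted, a true 25% is counted as 25% to 18%, and the chance of escalating after six subjects lies between 0.18 and 0.31. This assumes uniform onset on nominal days and that every late finding is left out. The documents support neither an onset distribution nor the all-chemistry mix behind the upper end. The effect on decisions is clearest at n = 6, at 3/6 and 1/6. A general claim that one missed event always moves Table 5 is not supported. Because this endpoint drives escalation and the sample is already scheduled, the text should be changed.

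**What to change.** Reconcile 5.2.1.4, the Table 4 footnote, 8.1 and 8.4.1 with the flow chart. State that laboratory abnormalities on the already scheduled Cycle 2 Day 1 safety sample are attributed to Cycle 1 for the DLT endpoint, and add to the flow chart that this sample is taken before the Cycle 2 dose. Leave the toxicity criteria, their grades and their durations as they are.

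Do not rely on an end-of-Cycle-1 sample for subjects who never start Cycle 2. None is scheduled: footnote q moves laboratory draws with any dose hold, and the Treatment Discontinuation visit has no CBC or chemistry, the next being at the 30-day safety visit. Subjects who stop before Cycle 2 Day 1 therefore remain uncovered, and the text should say so.

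The cost is wording. No visit or sample is added for subjects who start Cycle 2. On the nominal schedule the DLT assessment waits one further day (Day 22 instead of Day 21), and the reported DLT rate may come out slightly higher.
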